### **11.3.5 Pregnancy Tests**

All pre-menses females and female subjects of childbearing potential will undergo serum pregnancy testing at Baseline and Week 12. In addition, urine pregnancy testing will be performed at Screening, prior to randomization at Baseline, and at Weeks 2, 4, 8 and 12. The urine pregnancy tests will be supplied by the CRO or CRO vendor.

## **11.4 Adverse Events**

### **11.4.1 Definition of Adverse Event**

An AE is any untoward medical occurrence in a patient or clinical investigation subject administered a medicinal product and which does not necessarily have a causal relationship with the study drug. AEs include any unfavorable and unintended illness, sign, symptom, clinically significant laboratory test abnormality, or disease temporally associated with the use of a

medicinal product that has appeared or worsened during the course of the clinical trial, regardless of causal relationship to the study drug(s) under study. AEs include any illness, sign, symptom, or out-of-range and clinically significant laboratory finding that has appeared or worsened during the course of the clinical trial, regardless of causal relationship to the study. The collection of non-serious AEs and serious adverse events (SAEs) will begin following the subject's completion of the consent process to participate in the study.

#### **11.4.2 Documenting Adverse Experiences**

It is the responsibility of the investigator to document all AEs that occur during the course of the study. The AEs should be documented as a single medical diagnosis. When this is not possible, the AE should be documented in terms of signs and/or symptoms observed by the investigator or reported by the subject at each study visit. Each AE which appears to be independent of any prior event will be reported separately.

All AEs occurring after the subject signs the informed consent through the last study visit must be reported, regardless of whether or not the AEs are considered drug-related. All AEs, whether in response to a query, observed by the study site personnel, or reported spontaneously by the subject, will be recorded. Any AEs deemed related to treatment reported or observed at the final study/treatment visit will be followed until stabilization or resolution (or up to 30 days after final study visit).

At each visit during the study, the subject will be assessed for the occurrence of new and ongoing AEs. Cutaneous tolerability signs and symptoms that result in the subject's requiring a concomitant therapy, interruption of treatment, or discontinuation from the study will be reported as an AE. The following data will be collected on all AEs and recorded on the appropriate eCRF:

- Event name (diagnosis preferred, if unknown, record the signs/symptoms)
- Onset date and end date
- Maximum intensity (severity)
- Seriousness
- Action taken regarding study drug
- Corrective treatment, if given
- Outcome

In addition, the investigator's assessment of causality will be recorded.

Vital sign abnormalities are to be recorded as AEs only if they are clinically significant (for example: are symptomatic, requiring corrective treatment, leading to discontinuation or fulfilling a seriousness criterion).

### 11.4.3 Serious Adverse Events

All AEs will be assessed as either serious or non-serious.

An SAE or serious adverse event is defined as any untoward medical occurrence that at any dose:

- Results in death
- Is immediately life threatening, (the term "life threatening" in the definition of "serious" refers to an event in which the subject is at risk of death at the time of the event; it does not refer to an event which hypothetically might have caused death if it were more severe)
- Requires in patient hospitalization or prolongation of existing hospitalization (hospitalization for elective surgery for a baseline condition is not considered an AE)
- Results in persistent or significant disability/incapacity (permanent or substantial disruption of a person's ability to conduct normal life functions)
- Is a congenital anomaly/birth defect
- Is a medically important event that may not be immediately life threatening or result in death or hospitalization, but may jeopardize the subject and may require medical or surgical intervention to prevent one of the above listed outcomes. Examples of such events include, but are not limited to, allergic bronchospasm requiring intensive treatment in an emergency room or at home; blood dyscrasias or convulsions that do not result in inpatient hospitalization.

Note: A spontaneous abortion, elective abortion and an ectopic pregnancy will be considered SAEs, and must be reported per Reporting of SAEs under Section 11.4.6.

### 11.4.4 Assessment of Severity

The severity assigned to an AE should be determined by the maximum severity of the AE. The categories described below should be used to estimate the severity of AEs:

- Mild: Awareness of a sign of symptom but is easily tolerated, requires no treatment and does not interfere with subject's daily activities
- Moderate: Low level of concern to the subject and may interfere with daily activities, but can be relieved by simple therapeutic care
- Severe: Interrupts the subject's daily activity and requires systemic or other treatment

#### **11.4.5 Assessment of Causality**

The investigator should assess the relationship of the AE, if any, to the study drug as either “Related” or “Not Related”. The following should be taken into account when assessing AE/SAE causality:

**Related:** There is at least a reasonable possibility that the AE/SAE is related to the study drug. Reasonable possibility means that there is evidence to suggest a causal relationship between the drug and the AE.

**Not Related:** There is little or no reasonable possibility that the AE/SAE is related to the study drug. This assessment implies that the AE/SAE has little or no temporal relationship to the study drug and/or a more likely or certain alternative etiology exists.

#### **11.4.6 Reporting of Serious Adverse Events**

Adverse events classified as “serious” require expeditious handling and reporting to sponsor or designee within 24 hours of investigational center notification to comply with regulatory requirements.

All SAEs, whether related or unrelated to study drug, must be immediately reported to the medical monitor and CRO contact within 24 hours of the investigator’s awareness of the event. All SAEs must be reported via confirmed facsimile or email transmission and must be submitted on a written SAE report form signed by the investigator within 24 hours of the investigator’s awareness of the event.

The contact(s) for reporting an SAE are:

Investigators should not wait to receive additional information to fully document the event before notifying Medical Monitor and Sponsor of an SAE. If only limited information is initially available, follow-up reports are required. Additional relevant information such as hospital records and autopsy reports should be provided to the Sponsor as soon as they are available. Should the investigator become aware of an SAE (regardless of its relationship to investigational

product) that occurs within 30 days after stopping the study drug, the SAE must be reported in accordance with procedures specified in this protocol.

All deaths of subjects, regardless of cause, and which are known to the Investigator will be reported on the appropriate eCRF for up to 30 days after the administration of study drug, regardless of the Investigator's opinion regarding drug relationship. Documentation of the subject's cause of death and a copy of the autopsy or hospital report will also be provided. The Medical Monitor and CRO contact must be notified within 24 hours of knowledge of the event by telephone (and/or facsimile/email) of all subject deaths. Written follow-up must be received by the medical monitor and the Institutional Review Board/Independent Ethics Committee (IRB/IEC) within five (5) calendar days of initial notification.

The investigator should take all appropriate measures to ensure the safety of the subjects, notably he/she should follow a subject with an SAE until the event has resolved or the condition has stabilized. This may imply that follow-up will continue after the subject has left the study, and that additional investigations may be requested by the Sponsor. When a SAE persists at the end of the study, the Investigator will conduct follow-up contacts with the subject until the Investigator/Sponsor agree the event is satisfactorily resolved and/or stabilized. If at any time after 30 days after administration of study drug, the investigator becomes aware of an SAE which he/she feels is related to study drug or procedure, this must also be reported immediately (within 24 hours of knowledge of occurrence) by telephone and confirmed facsimile transmission/email to the Medical Monitor and Sponsor and/or Sponsor designee.

#### **11.4.7 Expedited Serious Adverse Event Reports**

An AE, whether serious or non-serious, is designated unexpected (unlabeled) if it is not reported in the clinical safety section of the Investigator Brochure or if the event is of greater frequency, specificity or severity.

Expedited SAE reports are those that are both unexpected based on the reference document (Investigator Brochure) and are related (ie, the relationship cannot be ruled out) to the study drug. These expedited reports are subject to reporting timelines of 7 and/or 15 calendar days to the regulatory reporting agency(ies). The Sponsor will notify regulatory authorities of these AEs and all participating investigational centers in writing for submission by the investigator to the IRB/IEC. This notification will be in the form of a Safety Update to the Investigator Brochure (ie, "15-day letter").

Upon receiving such notices, the investigator must review and retain the notice with the Investigator Brochure and immediately submit a copy of this information to the responsible IRB/IEC according to local regulations. The investigator and IRB/IEC will determine if the informed consent requires revision. The investigator should also comply with the IRB/IEC procedures for reporting any other safety information.

#### 11.4.8 Pregnancy

All pre-menses females and female subjects of childbearing potential must use an effective method of birth control during the course of the study, in a manner such that risk of contraceptive failure is minimized. Abstinence is allowed as a birth control method.

Before enrolling a pre-menses female or female subject of childbearing potential in this clinical trial, the investigator must review the following information about study participation:

- Informed consent requirements
- Contraceptives in current use

Following review of this information and appropriate subject counseling, the investigator or designee and the subject must sign the informed consent before study enrollment.

During the study, all female subjects of childbearing potential should be instructed to contact the investigator immediately if they suspect they might be pregnant (eg, missed or late menstrual period).

If a subject or investigator suspects that the subject may be pregnant prior to study enrollment, the study drug must be withheld until the results of laboratory pregnancy testing are available. If pregnancy is confirmed, the subject must not receive study drug and must not be enrolled in the study. If pregnancy is suspected while the subject is receiving study treatment, the study drug must immediately be withheld until the result of pregnancy testing is known. If pregnancy is confirmed, the study drug will be permanently discontinued and the subject will be followed until the pregnancy comes to term. A Pregnancy Report form will be submitted to the sponsor, initially and at the end of the pregnancy, which includes the outcome of the pregnancy and any complications occurring during the pregnancy or the delivery.

All confirmed pregnancies must be immediately reported to the medical monitor and CRO contact within 24 hours of the investigator's awareness of the pregnancy. All confirmed pregnancies are to be reported on a pregnancy form using the same reporting procedure for an SAE under Section 11.4.6. If a pregnancy is associated with an SAE, the event should be reported on an SAE form and a pregnancy form as per procedure outlined in Section 11.4.6.

## 12 Statistics

All statistical processing will be performed using SAS® version 9.3 or later unless otherwise stated. Statistical significance will be based on two-tailed tests of the null hypothesis resulting in p-values of 0.05 or less.

The primary method of handling missing efficacy data will be based on estimation using the method of Markov Chain Monte Carlo (MCMC) imputation. This method provides robust estimation when the pattern of missingness is arbitrary. Additionally, the estimation will be done

for each treatment group separately so that the pattern of missingness for one group does not influence the estimation of missing data for another group. Groups of complete datasets following the estimation will be concatenated to form analysis datasets for the comparative analyses and subsequent imputation result inference with SAS PROC MIANALYZE. Descriptive statistics will also be derived from the multiply imputed datasets.

Additionally, a model-based multiple imputation process will be used as a sensitivity analysis to the MCMC imputation. The absolute change in lesion count will also be analyzed using a repeated measures ANCOVA for lesion count data or a repeated measures logistic regression model (generalized estimating equations) for the dichotomized EGSS. Finally, a tipping point analysis will be performed for the primary endpoints.

A statistical analysis plan (SAP), describing all statistical analyses will be provided as a separate document. The SAP will be finalized prior to unblinding of the study treatments.

#### Evaluations and Analyses

Inflammatory lesions and non-inflammatory lesions will be recorded for each subject at Baseline and at Weeks 2, 4, 8, and 12. The absolute and percent change from baseline of inflammatory lesions and non-inflammatory lesions will be derived for each subject at Weeks 2, 4, 8, and 12.

The EGSS will be recorded for each Subject. The EGSS will be dichotomized into “success” and “failure” at Week 2, 4, 8 and 12 with a subject considered a success for those visits if the EGSS is at least 2 grades less than baseline and are Clear or Almost Clear.

Subjects will be asked to complete the Acne-Specific Quality of Life Questionnaire at Baseline and Week 12.

All assessments will be conducted for both ITT and PP.

### **12.1 Assessment of Efficacy**

Primary, secondary, and supportive efficacy analyses will be conducted on the ITT (primary) population. Primary efficacy analyses will be conducted on the PP (supportive) population.

#### **12.1.1 Primary Efficacy**

There are three co-primary efficacy endpoints:

- Absolute change in inflammatory lesion count from Baseline to Week 12
- Absolute change in non-inflammatory lesion count from Baseline to Week 12
- Percentage of subjects who achieve at least a two-grade reduction at Week 12 from Baseline in the Evaluator's Global Severity Score and were Clear or Almost Clear

#### **12.1.2 Secondary Efficacy**

The secondary efficacy endpoints will be the following:

- Percent change in non-inflammatory lesion count from Baseline to Week 12

- Percent change in inflammatory lesion count from Baseline to Week 12
- Percentage of subjects who have at least a 2 grade reduction at Week 12 from Baseline in the Evaluator's Global Severity Score
- Percent change in non-inflammatory lesion count from Baseline to Week 8
- Percent change in inflammatory lesion count from Baseline to Week 8
- Percent change in non-inflammatory lesion count from Baseline to Week 4
- Percent change in inflammatory lesion count from Baseline to Week 4

### 12.1.3 Supportive Efficacy

The supportive efficacy endpoints will be as follows:

- Percent change in non-inflammatory lesion count from Baseline to Week 2
- Percent change in inflammatory lesion count from Baseline to Week 2
- Percentage of subjects who have at least a 2 grade reduction at Week 8 from Baseline in the Evaluator's Global Severity Score
- Percentage of subjects who have at least a 2 grade reduction at Week 4 from Baseline in the Evaluator's Global Severity Score
- Percentage of subjects who have at least a 2 grade reduction at Week 2 from Baseline in the Evaluator's Global Severity Score

### 12.1.4 Test of Superiority for Lesion Count Variables

This section provides the basic model and statistical approach which is used in combination with the multiple imputation procedures described in Section 12.1.9. Tests of superiority for the absolute change from Baseline in inflammatory and non-inflammatory lesions will be based on either parametric or non-parametric methods consistent with the statistical assumptions required to support the analyses. Specifically, the tests of superiority will be based on an ANCOVA with factors of treatment and analysis center and the respective Baseline lesion count as a covariate or on ranked data submitted to an ANCOVA with factors of treatment and analysis center and the respective Baseline lesion count as a covariate. If the treatment-by-analysis center interaction effect is significant at an alpha less than 0.10, then the effect will be included in the model; otherwise it will be removed.

A skewness test, based on the methods presented by J.H. Zar (1984) [10], will be applied to the residuals resulting from an ANCOVA. A two-sided p-value for the skewness test significant at 0.01 will imply the use of the non-parametric method. If a parametric analysis is indicated, the results of the parametric analysis will be considered the primary analysis. Should a non-parametric analysis be indicated, the absolute or percent changes in inflammatory and non-inflammatory lesions will be rank transformed prior to submitting them to the ANCOVA. Results of the rank-transformed analyses then will be considered the primary analysis; however, results of the non-ranked transformed analyses will also be presented.

### 12.1.5 Test of Superiority for EGSS

The EGSS will be dichotomized into “success” and “failure” with a subject considered a success for those visits if the Evaluator’s Global Severity Score is at least 2 grades less than Baseline and are Clear or Almost Clear. The analysis of the dichotomized Evaluator’s Global Severity Score will be based on a logistic regression test with factors of treatment group and analysis center.

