**Statistical methods:**

All statistical processing will be performed using SAS® version 9.3 or later unless otherwise stated. Statistical significance will be based on two-tailed tests of the null hypothesis resulting in p-values of 0.05 or less. Tests of lesion count superiority will be based on an ANCOVA with factors of treatment and analysis center and the respective Baseline lesion count as a covariate or on ranked data submitted to an ANCOVA with factors of treatment and analysis center and the respective Baseline lesion count as a covariate. The co-primary analysis of the dichotomized EGSS will be based on logistic regression with factors of treatment group and analysis center. The primary method of handling missing efficacy data will be based on estimation using the method of Markov Chain Monte Carlo (MCMC) imputation.

Additionally, a model-based multiple imputation process will be used as a sensitivity analysis to the MCMC imputation. The absolute change in lesion count will also be analyzed using a repeated measures ANCOVA for lesion count data or repeated measures logistic regression model (generalized estimating equations) for the dichotomized EGSS. Finally, a tipping point analysis will be performed for the primary endpoints.

Inflammatory and non-inflammatory lesion counts will be recorded for each Subject at Baseline and at Weeks 2, 4, 8, and 12. The absolute and percent change from Baseline in inflammatory and non-inflammatory lesions will be derived for each Subject at Weeks 2, 4, 8, and 12.

The EGSS will be recorded for each Subject. The EGSS will be dichotomized into “success” and “failure” with a Subject considered a success if the Evaluator’s Global Severity Score at Week 2, 4, 8, and 12 is at least 2 grades less than baseline and Clear or Almost Clear.

*Populations Analyzed:*

An intent-to-treat (ITT) analysis will be conducted on all study subjects. The ITT population will consist of all randomized subjects who were dispensed study drug.

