### 9.2 Randomization and Blinding

The study drugs will be packaged and labeled identically, and the study drug kits will be numbered sequentially and dispensed randomly via IWRS to the subjects entering the study within each investigational center. Study drug supplies will be distributed to the investigational centers to maintain the randomization ratio within each investigational center.

As a double-blinded study, the investigators, the site staff, the sponsor, and the clinical monitors will not be aware of the treatment assigned to the individual study subjects. Delegated staff members at each investigational center will dispense the study drugs and will collect all used and unused study drug pumps as scheduled.

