### 12.1.6 Statistical Hypothesis Testing and Control of Multiplicity

Statistical hypothesis testing for lesion count analyses will use the statistical model introduced in Section 12.1.4 and employs the methods of Section 12.1.9 regarding missing values. The analysis of the dichotomized Evaluator’s Global Severity Score will be based on the logistic regression with factors of treatment group and analysis center and employs the methods of Section 12.1.9 regarding missing values.

The overall Type I error will be controlled by requiring the three co-primary efficacy endpoints to be statistically significant. Specifically, failure of any one of the primary efficacy endpoints will invalidate the statistical significance of the secondary efficacy endpoints.

The following stepwise process will be conducted for testing the secondary efficacy endpoints in order to control for multiplicity. These tests will be performed for only the ITT population. The testing process will terminate whenever a statistical test for a step is not significant. All subsequent tests for the remaining steps will be considered not significant. The order of testing is:

Step Number	Secondary Endpoint
1	Percent change in non-inflammatory lesion count from Baseline to Week 12
2	Percent change in inflammatory lesion count from Baseline to Week 12
3	Percentage of subjects who have at least a 2 grade reduction at Week 12 from Baseline in the Evaluator’s Global Severity Score
4	Percent change in non-inflammatory lesion count from Baseline to Week 8
5	Percent change in inflammatory lesion count from Baseline to Week 8
6	Percent change in non-inflammatory lesion count from Baseline to Week 4
7	Percent change in inflammatory lesion count from Baseline to Week 4

The following stepwise process will be conducted for testing the supportive efficacy endpoints in order to control for multiplicity. These tests will be performed for only the ITT population. In order to control for multiplicity, failure of any one of the secondary efficacy endpoints will invalidate the statistical significance of the supportive efficacy endpoints. The testing process

will terminate whenever a statistical test for a step is not significant. All subsequent tests for the remaining steps will be considered not significant. The order of testing is:

Step Number	Supportive Endpoint
1	Percent change in non-inflammatory lesion count from Baseline to Week 2
2	Percent change in inflammatory lesion count from Baseline to Week 2

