**Syntax:**

```
proc mi data=datain out=dataout seed=&seed. nimpute=5 <options>;
  where trtpn=(1, or 2);
```

```

mcmc chain=multiple;
var baseline week2 week4 week8 week12;
run;

```

2. For each complete data set, the dichotomous success rate (clear or almost clear with a 2-point change from baseline) will be computed. The 12-week imputed EGSS values will be rounded to the nearest integer value prior to evaluating the success rate. Each complete data set will be analyzed with a logistic regression with factors of treatment group and analysis center.
4. The results from these analyses will be combined into a single inference using SAS PROC MIANALYZE.

A total of 2 random seeds will be needed to impute EGSS for the two treatment groups. Those 2 random seeds have been pre-specified by using a random number generator:

- EGSS; IDP-120 Gel: Seed= 923694678
- EGSS; IDP-120 Vehicle: Seed= 802843905

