#### Sensitivity analyses for EGSS

The first sensitivity analysis for the dichotomized EGSS success will use a repeated measures logistic regression model (generalized estimating equations), with dichotomized EGSS success as the dependent variable and treatment, analysis center, and visit (ie, Week 4, Week 8) as independent factors. In this analysis, data from all post-baseline visits will be included with no imputation for missing data.

The second sensitivity analysis will use the model based multiple imputation method to impute missing data for the dichotomized EGSS data. Although the full details will be presented in the SAP, the multiple imputation will involve 3 principal tasks:

1. Missing values will be filled in 5 times to generate 5 data sets. The imputation model used logistic regression with factors of treatment group and analysis center (ie, the imputation model will be the same as the analysis model).
2. Each complete data set will be analyzed with a logistic regression a factors of treatment group and analysis center.
3. Results from these analyses will be combined into a single inference using SAS PROC MIANALYZE.

A total of 1 random seed will be needed. The random seed has been pre-specified by using a random number generator:

- EGSS: Seed= 461039866

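### The EGSS co-primary model omits baseline EGSS grade (3 or 4), although both lesion-count co-primaries adjust for baseline; the planned test is valid, and adding the factor is a small, cheap gain

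*Combined protocol and SAP*

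**What the plan says.** The EGSS co-primary model has the same two factors wherever it appears:

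- Synopsis, Statistical methods: the analysis "will be based on logistic regression with factors of treatment group and analysis center".
- Section 12.1.5: it "will be based on a logistic regression test with factors of treatment group and analysis center".
- Section 12.1.6: it "will be based on the logistic regression with factors of treatment group and analysis center".
- Section 12.1.9, EGSS imputation, step 2: "Each complete data set will be analyzed with a logistic regression with factors of treatment group and analysis center".

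The sensitivity analyses in Section 12.1.10 follow suit. The GEE is fitted "with dichotomized EGSS success as the dependent variable and treatment, analysis center, and visit" as the independent factors. For the model-based imputation, "The imputation model used logistic regression with factors of treatment group and analysis center", and its analysis model is the same.

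The lesion counts are handled differently. Section 12.1.4 fits treatment, analysis center "and the respective Baseline lesion count as a covariate", and the lesion-count repeated-measures and model-based imputation analyses in Section 12.1.10 also include baseline count.

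Baseline EGSS otherwise enters the variable list of the MCMC imputation (12.1.9), the definition of success, and descriptive tables (12.1.7, 12.1.11). On allocation, Section 9.2 says drug supplies are distributed "to maintain the randomization ratio within each investigational center"; no stratification by grade is described.

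**The concern.** Section 8.1 admits only grades 3 and 4. Success needs a score of 0 or 1 at Week 12 together with a drop of at least two grades. For a grade-3 subject, reaching 0 or 1 is a drop of at least two grades; for a grade-4 subject it is at least three. The definition itself therefore makes baseline grade a likely predictor of success, and nothing in the documents explains why this co-primary alone goes without its baseline.

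Two things are at stake, both modest. The first is power: EGSS is planned at about 95%, the lesion counts at over 99% (12.8.2), and all three must be significant (12.1.6), so EGSS is where extra precision is worth most. The second is the single realised result: a chance difference between arms in the share of severe subjects would move the unadjusted estimate. The tables in 12.1.7 and 12.1.11 would show such a difference but would not adjust for it.

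**Working it through.** **Inputs from the plan.** Success rates 26.6% and 14.3%, 293 per group required and 300 used (12.8.2); two-sided 0.05 (Section 12); 1:1 allocation (9.1).

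**Assumptions, not in the documents.** Grade-4 share q of 12–30%; odds ratio of success, grade 4 against grade 3, of 0.25–0.5; a smaller true effect of 23.0% vs 14.3% as a second scenario. Each arm's overall rate is held fixed whatever q and the odds ratio. Center is left out of the large-sample calculation.

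**1. The plan's own figure.** With mean rate 0.2045,

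n = [1.960·√(2·0.2045·0.7955) + 1.645·√(0.266·0.734 + 0.143·0.857)]² / 0.123² = 276.5.

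With continuity correction, (n/4)·[1 + √(1 + 4/(n·0.123))]² = 292.5, so 293. The stated size reproduces.

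**2. Power without baseline EGSS, 300 per arm.** Log odds ratio = ln[(0.266/0.734)/(0.143/0.857)] = 0.7756 (odds ratio 2.17). SE = √[1/(300·0.266·0.734) + 1/(300·0.143·0.857)] = 0.2104. Power = Φ(0.7756/0.2104 − 1.960) = Φ(1.726) = 95.8%. At 23.0% vs 14.3%: 0.5823/0.2145 = 2.714, power 77.5%.

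**3. Power with baseline EGSS.** For each q and odds ratio, the intercepts are solved so that (1−q)·(grade-3 rate) + q·(grade-4 rate) equals the arm's overall rate. The SE comes from the information matrix for intercept, treatment and grade.

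| Grade-4 share | Odds ratio, 4 vs 3 | Conditional treatment OR | Power at 26.6% vs 14.3% | Power at 23.0% vs 14.3% |
|---|---|---|---|---|
| any | 1 (not prognostic) | 2.17 | 95.8% | 77.5% |
| 12% | 0.5 | 2.18 | 95.9% | 77.7% |
| 12% | 0.25 | 2.20 | 96.0% | 78.0% |
| 30% | 0.5 | 2.19 | 96.0% | 78.0% |
| 30% | 0.25 | 2.24 | 96.4% | 79.0% |

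The gain is 0.1–0.6 points at the planned rates and 0.2–1.5 points at the smaller effect. Stretching the odds ratio to 0.1 with 30% severe gives 96.9% at the planned rates.

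**4. Chance imbalance.** The SD of the between-arm difference in severe share is √[2q(1−q)/300]: 2.65 points at q = 0.12 and 3.74 at q = 0.30. The probability of a difference of 4 points or more, 2·[1 − Φ(4/SD)], is 13% and 29%.

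A 4-point difference (2 points either side of q) shifts the expected success-rate difference by 0.02 × (grade-3 minus grade-4 rate, summed over arms):

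- q = 0.12, odds ratio 0.5: 0.02·[(0.151 − 0.082) + (0.280 − 0.163)] = 0.4 points.
- q = 0.30, odds ratio 0.25: 0.02·[(0.182 − 0.053) + (0.333 − 0.111)] = 0.7 points.

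The SE of the difference is √[(0.266·0.734 + 0.143·0.857)/300] = 3.25 points, so the shift is 0.1–0.2 SE.

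**5. Simulation with centers.** 4,000 trials per scenario, 28 unequal centers with at least 5 per arm, center SD 0.3 on the logit scale; rejection rates without and with baseline EGSS:

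| Scenario | 12% severe, OR 0.4 | 30% severe, OR 0.25 |
|---|---|---|
| 26.6% vs 14.3% | 96.9% / 97.2% | 97.0% / 97.8% |
| 23.0% vs 14.3% | 81.2% / 81.7% | 79.8% / 80.7% |
| No treatment effect | 5.1% / 5.2% | 6.2% / 5.9% |

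The simulation SE of the null rates is about 0.35 points. A separate simulation without center, 6,000 trials per scenario, gave type I error of 4.6–5.3% unadjusted and 4.5–5.2% adjusted.

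**The case against.** The strongest reply is that nothing is broken. The test is valid, 300 per arm already exceeds the 277 needed without continuity correction, and the benefit may be nil: if grade is not prognostic the gain is zero, and the top figure of 1.5 points needs 30% severe, an odds ratio of 0.25 and a 23.0% active rate together. A 4-point imbalance moves the estimate by only a small fraction of its SE. The parallel with lesion counts is also loose, since those vary widely at baseline (20–50 and 25–100) while EGSS has two adjacent grades. The primary MCMC imputation already uses baseline EGSS, and 12.1.10 leaves the full details of the model-based imputation to the SAP.

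All of that stands as a limit on importance. It does not argue for leaving the factor out, because including it costs essentially nothing when grade is not prognostic.

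Two further points are fair. The simulated type I error of 6.2% is above 5% by more than simulation error. Excess of this size appears with and without baseline EGSS and disappears when center is dropped, so it comes from fitting many small centers, and the simulated powers near 97% partly reflect it. Also, the EGSS interaction models in 12.1.8 would lack a factor that the primary model then has; adding it there too is a harmless extension.

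**Conclusion.** The point holds as a worthwhile refinement, not as an error. The co-primary EGSS model, its GEE and its model-based imputation omit an already recorded, probably prognostic two-level factor, while the lesion-count models include theirs. The expected gain is 0.1–0.6 points of power at the planned rates and 0.2–1.5 points at 23.0% vs 14.3%, falling to zero if grade is unrelated to success, with a little protection against chance imbalance in severity. These sizes rest on an assumed severe share and an assumed effect of grade. The omission, the contrast with the lesion counts and the unequal drop required of the two grades come directly from the documents.

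**What to change.** In the Synopsis and Sections 12.1.5, 12.1.6 and 12.1.9 (EGSS step 2), specify the co-primary EGSS model as *logistic regression on treatment, analysis center and baseline EGSS grade (3 or 4)*. In Section 12.1.10, add baseline EGSS to the GEE and to both the imputation and the analysis step of the model-based method. Keep the model without baseline EGSS as a sensitivity analysis. For consistency, the EGSS interaction models in 12.1.8 can carry the same factor. The change need not extend to the endpoints defined only by a two-grade reduction, where both grades need the same drop.

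The cost is one factor in text and code, with no extra data or subjects. Section 12 has the SAP finalized before unblinding; the factor should be fixed by then, since adding it after an imbalance is seen would look post hoc. The one downside is that the treatment odds ratio becomes conditional on baseline grade as well as center (2.18–2.24 against 2.17 under the assumptions above), which the report should state.
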